### **Ethical Considerations**

The study was approved by the Ethics Committee of the Federal University of Santa Catarina (approval number 6.040.767). All participants were informed about the procedures, risks, and benefits of the research and provided written informed consent prior to participation.

### **Expected Results**

It was expected that systolic blood pressure would show a significant reduction 45 minutes after the experimental session, while diastolic blood pressure would remain unchanged. Heart rate was anticipated to increase immediately after the pole dance session, followed by a gradual return to baseline values during the recovery period.

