**NCT number: [to be filled after registration]**

**Document date:22/07/2022**

## **Study Protocol and Statistical Analysis Plan**

### **Introduction**

Pole dance (PD) combines aerobic and isometric components, with potential to influence cardiovascular variables. The primary objective of this study was to evaluate the acute blood pressure response after a single PD session in young normotensive women. The hypothesis was that a PD session would promote post-exercise hypotension for systolic blood pressure (SBP), without significant changes in diastolic blood pressure (DBP).

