### **Study Design**

This was an experimental, randomized study with a control session. The sample consisted of 21 women practicing pole dance at an intermediate level. Each participant performed two sessions on different days: one experimental session, which consisted of a 60-minute pole dance class, and one control session, which consisted of 60 minutes of seated rest without physical effort. The order of the sessions was defined randomly to ensure balance and minimize bias.

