### **Statistical Analysis Plan**

Data analysis was performed using SPSS version 17.0. Descriptive statistics were used to characterize the sample, with continuous variables expressed as mean and standard deviation, and categorical variables expressed as absolute and relative frequencies. Differences in systolic blood pressure, diastolic blood pressure, and heart rate between sessions and across time points were analyzed using repeated measures ANOVA (session  $\times$  time), followed by Bonferroni post-hoc tests. Spearman's correlation coefficient was applied to examine associations between blood pressure, heart rate, and perceived exertion. A significance level of  $p < 0.05$  was adopted for all analyses.

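### The plan predicts that SBP falls while DBP does not, but never compares the two effects, so an equal fall in both pressures could be reported as an SBP-only response.

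*Combined protocol and SAP*

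**What the plan says.** The Introduction hypothesises that "a PD session would promote post-exercise hypotension for systolic blood pressure (SBP), without significant changes in diastolic blood pressure (DBP"). Expected Results gives the same pattern a time point: "systolic blood pressure would show a significant reduction 45 minutes after the experimental session, while diastolic blood pressure would remain unchanged".

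The Statistical Analysis Plan states: "Differences in systolic blood pressure, diastolic blood pressure, and heart rate between sessions and across time points were analyzed using repeated measures ANOVA". The factors are session and time, "followed by Bonferroni post-hoc tests", and the significance level is 0.05. The only other planned analysis involving blood pressure is a set of Spearman correlations with heart rate and perceived exertion. No factor, contrast or derived variable sets the SBP effect against the DBP effect. No margin is given for DBP.

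Study Design gives the size and the pairing: "The sample consisted of 21 women practicing pole dance at an intermediate level", and "Each participant performed two sessions on different days". Under Procedures, blood pressure is read at five time points. The Timeline section reports the analyses as already finalized.

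**The concern.** The prediction concerns a pattern across two outcomes: one pressure moves and the other does not. Under the plan as written, it would be judged confirmed by SBP p < 0.05 together with DBP p ≥ 0.05. A significant result beside a non-significant one is not evidence that the two effects differ. If the class lowers both pressures by the same amount, sampling variation in 21 women can put one p-value below the threshold and the other above it.

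This is separate from the question of whether DBP on its own can be called unchanged. Giving DBP an equivalence margin, or softening its wording, would still leave untested whether SBP fell by more than DBP. At stake is a dissociation between the pressures being reported as the confirmed hypothesis when there was none.

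**Working it through.** The documents state no effect size, SD, SBP–DBP correlation or power, so there is no planned figure to reproduce. The check asks how often equal true effects give the hypothesised pattern.

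**Inputs from the documents:** n = 21 paired (Study Design); α = 0.05 (Statistical Analysis Plan), taken as two-sided because sidedness is not stated; comparison at 45 minutes (Expected Results).

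**Assumed inputs:** SD of the class-minus-control difference 8 mmHg for SBP and 6 or 8 for DBP; correlation ρ of the two differences 0.3 to 0.7; equal true falls of 3, 4 or 5 mmHg.

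**Step 1, power for each pressure.** Paired t-test with 20 df and noncentrality (fall/SD) × √21. For a 4 mmHg fall:
- SD 8: 0.500 × 4.583 = 2.29, power about 0.59.
- SD 6: 0.667 × 4.583 = 3.06, power about 0.83.

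**Step 2, the false pattern if the pressures were uncorrelated.** P = power(SBP) × [1 − power(DBP)].
- SD 8/8: 0.587 × 0.413 = 0.24.
- SD 8/6: 0.587 × 0.172 = 0.10.

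**Step 3, with correlation.** Bivariate normal simulation, at least 40,000 trials per setting. At a 4 mmHg fall and ρ = 0.5, the pattern occurs in 17% of trials (8/8) and 5% (8/6). Over falls of 3–5 mmHg and ρ of 0.3–0.7:

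| Assumed SD, SBP/DBP | SBP significant, DBP not (α = 0.05) | Same, at α = 0.005 | Pattern plus significant pulse-pressure contrast (α = 0.05) |
|---|---|---|---|
| 8/6 | 1–11% | 3–9% | about 2% or less |
| 8/8 | 10–20% | 6–20% | about 2% or less |

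The 0.005 column is 0.05/10, a Bonferroni illustration; the plan does not state the number of comparisons. If SBP differences were instead the less variable (6/8, 4 mmHg, ρ = 0.5), the pattern would occur in 29%.

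**Step 4, the direct contrast.** Pulse pressure is SBP minus DBP, so the variance of its paired difference is σ_S² + σ_D² − 2ρσ_Sσ_D. At ρ = 0.5:
- 8/6: 64 + 36 − 48 = 52, SD 7.2.
- 8/8: 64 + 64 − 64 = 64, SD 8.

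Under equal falls in mmHg the contrast rejects in 5% of trials, so 2.5% in the SBP direction. That caps the false claim that SBP fell more. When the truth is SBP −5 and DBP 0, its power is about 85% (8/6) or 78% (8/8), against 78% for SBP itself.

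**Step 5, what the contrast costs.** With SBP −5 and DBP 0, SBP significant and DBP not occurs in about 74% of trials. Also requiring the contrast gives:

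| SD, SBP/DBP | ρ = 0.5 | ρ = 0.3 |
|---|---|---|
| 8/6 | 70% | 64% |
| 8/8 | 63% | 55% |

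**Step 6, what the contrast cannot show.** Take true falls of 10 (SBP) and 5 mmHg (DBP), SD 8/6, ρ = 0.5. SBP and the contrast are both significant in about 86% of trials, and in 81% of trials DBP falls significantly as well. The contrast supports a larger SBP fall, not an SBP-only one.

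**Step 7, scale.** Equal proportional falls are not null for pulse pressure. As an illustration, 4% of an assumed 120/75 mmHg is 4.8 and 3 mmHg. The contrast then rejects toward SBP in 15–28% of trials (8/6, ρ 0.3–0.7).

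**The case against.** The strongest reply is that the documents never call the response specific or selective, and never say that the SBP effect exceeds the DBP effect. They make two statements, one per pressure, and the second calls for a DBP interval judged against a margin. A pulse-pressure contrast answers a question the authors did not pose. This stands in part. A reader might infer that an SBP-specific response is the stated hypothesis, but the wording does not go that far. It does predict a fall in one pressure alongside no change in the other, and a report that finds this pattern will naturally be read as a dissociation. The plan has nothing to support that reading.

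Three further points stand:
- The risk is small in some settings. At SD 8/6 it is as low as 1%, and nothing in the documents favours 8/8 over 8/6. It should not be called common.
- The contrast has limits. It does not establish that DBP is unchanged, it depends on the absolute mmHg scale, and it costs more power at 8/8 than at 8/6.
- The analyses are reported as finalized, so the contrast cannot now be presented as planned.

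The plan does not use the word separate for the SBP and DBP analyses. That makes no difference: a session-by-time model has no outcome factor, so the comparison is absent on any reading.

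**Conclusion.** The concern holds in a limited form. The plan predicts different behaviour of SBP and DBP and includes no test that they differ, so equal falls can be reported as an SBP-only response. Under equal true falls of 3–5 mmHg in 21 women, that happens in about 1–11% of trials (SD 8/6) or 10–20% (SD 8/8), for correlations of 0.3–0.7. The size rests wholly on assumed SDs, correlation and effects; the gap in the plan does not.

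A reader might go further and infer that the SBP finding itself is unsound. The documents do not support that: the comparison of SBP with control is a valid question in its own right and this point leaves it untouched. The defect is confined to the joint statement about the two pressures.

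**What to change.** 1. Compute pulse pressure (SBP minus DBP) at each reading. Report the class-minus-control differences at 45 minutes in SBP, DBP and pulse pressure, each with a 95% CI from the same model.
2. State that SBP fell by more than DBP, in absolute mmHg, only if SBP is significantly reduced and the pulse-pressure interval excludes zero in that direction. Otherwise report both effects without claiming that they differ.
3. Do not call the response SBP-only, or DBP unchanged, on the strength of this contrast or of a non-significant DBP test. Describe DBP by its estimate and CI, and bring the Introduction and Expected Results into line with this.
4. Label the contrast as added after data collection.

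The cost is one derived variable and some wording; no new readings or participants are needed. Because the contrast is examined only after SBP is significant, the SBP test loses no alpha. The price is the loss of power shown above when the effect truly is on SBP alone: with SBP −5 and DBP 0, the chance of supporting the selective pattern falls from about 74% to 64–70% (SD 8/6) or 55–63% (SD 8/8) at correlations of 0.3–0.5. The report should also say that the contrast is null only for equal absolute falls, not equal proportional ones.

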### **Timeline**

The study was conducted and completed in 2023. Data collection occurred during that year, with each participant performing both the experimental and control sessions on separate days. Blood pressure and heart rate were monitored for 45 minutes after each session, and statistical analyses were finalized following data collection.
